4. STUDY OBJECTIVES

4.1 Primary Objective

- To evaluate the relative bioavailability of LY2963016 compared to LANTUS following subcutaneous (SC) single-dose administrations (0.5 U/kg) in healthy Chinese subjects.

4.2 Secondary Objectives

- To evaluate the safety and tolerability of LY2963016 when administered to healthy Chinese subjects.
- To compare other PK parameters of LY2963016 with those of LANTUS after 0.5-U/kg SC administration.
- To compare the PD responses of LY2963016 with those of LANTUS after 0.5-U/kg SC administration.

5. STUDY DESIGN

This is a randomised, open-label, single-dose (0.5 U/kg), 2-treatment, 2-period, crossover, single-site, euglycaemic clamp study to evaluate the relative bioavailability of LY2963016 to LANTUS in healthy subjects. The study will have 2 treatment periods, with subjects randomly assigned in a 1:1 fashion to a treatment sequence of either LY2963016 (Period 1) followed by LANTUS (Period 2), or LANTUS (Period 1) followed by LY2963016 (Period 2) (Figure 1). Study drug will be administered once per period as an SC dose. Up to 60 healthy men and women will be enrolled in order to ensure that 40 subjects complete the study.

[figure not shown]

Figure 1. Study design

6. TREATMENTS

The following is a list of the study treatment abbreviations that will be used in the TFLs.

Study Treatment Name	Treatment order in TFL
----------------------	------------------------

LY2963016 0.5 U/kg SC	1
LANTUS 0.5 U/kg SC	2

7. SAMPLE SIZE JUSTIFICATION

Up to 60 healthy subjects may be enrolled to ensure that at least 52 subjects complete the study. Assuming the ratio of AUC between test and reference product is 1, with 52 subjects completing, there is 80% coverage probability that the half-width of the 90% confidence interval (CI) of the difference of means for the area under the concentration time curve (AUC) will be within 0.223 in the log scale, which corresponds to approximately 20% in the ratio scale. This precision estimate was based on the intrasubject variability for AUC of 39.26% observed in completed studies in healthy subjects. Drop-outs may be replaced and the replacement subject would assume the withdrawn subject's treatment sequence (receiving both allocated treatments).

8. DEFINITION OF ANALYSIS POPULATIONS

The “Safety” population will consist of all subjects who received at least one dose of study drug.

The “Pharmacokinetic” population will consist of all subjects who received at least one dose of study drug and have evaluable PK data.

The “Pharmacodynamic” population will consist of all subjects who received at least one dose of study drug and have evaluable PD data.

All protocol deviations that occur during the study will be considered for their severity/impact and will be taken into consideration when subjects are assigned to analysis populations.

9. STATISTICAL METHODOLOGY

9.1 General Considerations

Data listings will be provided for all data that is databased. Summary statistics and statistical analysis will only be presented for data where detailed in this SAP. For continuous data, summary statistics will include the arithmetic mean, arithmetic standard deviation (SD), median, min, max and N; for log-normal data (e.g. the PK parameters: AUCs and the maximum drug concentration [C_{max}]) the geometric mean and geometric coefficient of variation (CV%) will also be presented. For categorical data, frequency count and percentages will be presented. Data listings will be provided for all subjects up to the point of withdrawal, with any subjects excluded from the relevant population highlighted. Summary statistics and statistical analyses will generally only be performed for subjects included in the relevant analysis population. For the calculation of summary statistics and statistical analysis, unrounded data will be used.

Data analysis will be performed using SAS[®] Version 9.4 or greater.

9.2 Demographics and Subject Disposition

Subject disposition will be listed. The demographic variables age, sex, race, ethnicity, site ID, body weight, height and body mass index will be summarized and listed.

9.3 Pharmacokinetic Analyses

PK analyses will be conducted on the Pharmacokinetic population.

9.3.1 Pharmacokinetic Parameter Estimation

PK parameter estimates for LY2963016 and LANTUS will be calculated by standard noncompartmental methods of analysis using WinNonlin Phoenix software. The version of any software used for the analysis will be documented, and the program will meet the Lilly requirements of software validation.

The analyses will be performed according to the Lilly Global Pharmacokinetics, Pharmacodynamics, and Pharmacometrics Divisional Standards. For each profile, concentration values that are below the quantifiable limit of the assay will be imputed as $\frac{1}{2}$ LLOQ. Actual sampling times in individual subjects will be used in the analysis. The serum concentration of immunoreactive LY2963016 and LANTUS will be corrected for endogenous insulin using the C-peptide data. The primary parameters for PK analysis will be: AUC from time zero to 24 hours [AUC(0-24)] and C_{max} . Other PK parameters that will be reported include: AUC from time zero to last measured concentration value [AUC(0- t_{last})], AUC from time zero to infinity [AUC(0- ∞)], t_{max} , apparent clearance (CL/F), $t_{1/2}$, and the apparent volume of distribution (Vz/F). The AUC values will be calculated by the linear/log trapezoidal method, where the linear trapezoidal method will be employed up to t_{max} , and the log trapezoidal rule will be used for concentrations beyond t_{max} .

9.3.2 Pharmacokinetic Statistical Inference

The primary PK parameters, AUC(0-24) and C_{max} , will be log-transformed prior to analysis. A linear mixed effects model will be fitted to the data. The model will include subject as a random effect, with period, sequence, and treatment as fixed effects. For each PK parameter, the difference in least-square treatment means (LY2963016 – Lantus) along with the 90% confidence intervals (CIs) will be back-transformed to produce the ratio of geometric means and the CIs comparing LY2963016 to Lantus. Within subject coefficient of variation (CV) for each insulin may be reported if estimable. A similar statistical analysis will be performed for the log-transformed secondary PK parameters AUC(0- ∞) and AUC(0- t_{last}).

Example SAS code:

```
proc mixed data=pk;
  class subject period sequence treatment;
  model log_pk = period sequence treatment /solution ddfm=kr residual;
  random subject;
  lsmeans treatment / pdiff alpha=0.1;
  ods output lsmeans=lsm;
  ods output diff=diff;
```

run;

Exploratory analyses may be performed for other PK parameters as deemed appropriate. Descriptive statistics may be reported for other PK parameters as deemed appropriate (e.g, CL/F, Vz/F, $t_{1/2}$). Median t_{max} will be calculated per treatment and a nonparametric approach will be taken to evaluate the difference in median t_{max} , using the Wilcoxon signed-rank test. The difference in median t_{max} between treatments and the 95% CIs for the difference will be reported.

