Safety: Safety laboratory parameters, vital signs, ECG parameters, and AEs will be listed and summarised using standard descriptive statistics.

Statistical: The primary and secondary PK and PD parameters will be log-transformed prior to analysis. The model will include subject as a random effect, with period, sequence, and treatment as fixed effects. For each PK and PD parameter, the comparison will be evaluated as the ratio of the least-squares geometric means of test formulation (LY2963016) to reference formulation (LANTUS). The estimate of the ratio of means between the 2 treatments and the corresponding 90% confidence interval will be provided. Descriptive statistics will be reported for all PK and PD parameters.

3. Table of Contents

Relative Bioavailability of LY2963016 to LANTUS® after Single-Dose Subcutaneous Administration in Healthy Chinese Subjects

Section	Page
1. Protocol I4L-MC-ABEF(b) Relative Bioavailability of LY2963016 to LANTUS® after Single-Dose Subcutaneous Administration in Healthy Chinese Subjects.....	1
2. Synopsis	2
3. Table of Contents.....	4
4. Abbreviations and Definitions.....	9
5. Introduction	12
5.1. General Introduction	12
5.2. Rationale and Justification for the Study	14
6. Objectives	15
6.1. Primary Objective	15
6.2. Secondary Objectives.....	15
7. Investigational Plan.....	16
7.1. Summary of Study Design.....	16
7.1.1. Screening Visit.....	16
7.1.2. Study Periods 1 and 2.....	16
7.1.3. Follow-up Visit	17
7.2. Discussion of Design and Control	17
7.3. Determination of Sample Size	17
8. Study Population.....	19
8.1. Criteria for Enrolment	19
8.1.1. Inclusion Criteria	19
8.1.2. Exclusion Criteria	20
8.2. Discontinuation	21
8.2.1. Discontinuation of Subjects.....	21
8.2.2. Discontinuation of Study Sites	22
8.2.3. Discontinuation of the Study	22
9. Treatment.....	23
9.1. Rationale for Selection of Dose	23
9.2. Investigational Product Formulations	23

9.3. Investigational Product Administration.....	23
9.4. Specific Restrictions/Requirements	24
9.5. Blinding	25
9.6. Concomitant Therapy	25
10. Pharmacokinetic, Pharmacodynamic, and Safety Data Collection.....	26
10.1. Pharmacokinetic and Pharmacodynamic Evaluations.....	26
10.1.1. Samples for Pharmacokinetic and Pharmacodynamic Measurements	26
10.1.2. Bioanalysis.....	26
10.1.3. Pharmacodynamic Evaluations (Glucose Clamp Procedure).....	26
10.2. Samples for Standard Laboratory Testing	27
10.3. Safety Evaluations.....	28
10.3.1. Safety Measures	28

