5.1. General Introduction

LY2963016 (Basaglar®) is a long-acting human insulin analogue, having the same primary amino acid sequence as LANTUS® (insulin glargine) and similar in qualitative and quantitative composition to LANTUS.

LANTUS is a recombinant human insulin analogue administered as a subcutaneous (SC) injection that is indicated for once-daily (QD) SC administration for the treatment of patients with diabetes mellitus for the control of hyperglycaemia (LANTUS package insert, 2015).

Insulin glargine differs from human insulin in that the amino acid asparagine at position A21 is replaced by glycine, and 2 arginines are added to the C-terminus of the B-chain. These structural modifications effectively shift the isoelectric point of the molecule, which decreases solubility of the insulin glargine at the physiologic pH of SC tissues. Upon injection of the insulin glargine solution into the SC tissue, the acidic solution is neutralised, microprecipitates form, and small amounts of insulin glargine are slowly released. This results in a relatively constant plasma concentration of insulin glargine over 24 hours with no pronounced peak.

In a 4-week repeat-dose toxicology study, rats were administered QD SC doses of 0, 0.3, 1.0, and 3.0/2.0 mg/kg of LY2963016 or LANTUS. The dose-limiting toxicity was severe hypoglycaemia for both LY2963016 and LANTUS; based on this, the no-observed-adverse-effect level, and maximum tolerated dose was 0.3 mg/kg for both LY2963016 and LANTUS. Findings common to insulin analogues, including neuropathy, lipohypertrophy, and islet cell atrophy, were produced in rats by LY2963016 and LANTUS at identical doses and were related to hyperinsulinaemia or hypoglycaemia. While the margins of safety for hypoglycaemia are moderate in rats (15.9-fold), this is not unusual in the development of insulin analogues.

Chemical and biological activity testing demonstrated the similarity of LY2963016 drug product to LANTUS. LY2963016 and LANTUS have comparable binding affinity to human insulin receptor, isoform A (IR-A), human insulin receptor, isoform B (IR-B), and human insulin-like growth factor 1 receptor (IGF-1R), highly similar in vitro functional activity, and highly similar in vitro mitogenic potential.

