In 2 Phase 1 clinical studies, conducted in predominantly Caucasian healthy subjects, LY2963016 serum concentrations increased gradually following single SC doses of 0.5 U/kg, indicating a slow, prolonged absorption with median time to maximum serum study drug concentration (t_{max}) of 12 hours. The serum concentration-time profile was relatively flat and constant over 24 hours, with the geometric mean value for apparent terminal half-life ($t_{1/2}$) being approximately 10 hours.

The pharmacokinetic (PK) parameters area under the serum study drug concentration versus time curve (AUC) from zero to 24 hours (AUC[0-24]) and maximum serum concentration (C_{max}) of LY2963016, and the pharmacodynamic (PD) parameters total amount of glucose infused (G_{tot}) and maximum glucose infusion rate (GIR) (R_{max}) during a euglycaemic glucose clamp were similar to LANTUS and similar durations of action were observed.

Across 5 completed clinical pharmacology studies, conducted in predominantly Caucasian subjects, 209 healthy subjects received at least 1 dose of LY2963016 and 247 healthy subjects received at least 1 dose of LANTUS. When data were combined for all 5 studies, a total of 215 treatment-emergent adverse events (TEAEs; all causalities) were reported by 112 (53.6%) LY2963016-treated subjects and 327 TEAEs were reported by 149 (60.3%) LANTUS-treated subjects. The TEAEs that occurred in $\geq 5\%$ of subjects with either treatment were: headache, procedural site reaction, catheter site swelling, catheter site pain, and catheter site hematoma. The TEAEs that were judged by the investigator to be related to study drug that occurred in $\geq 1\%$ of subjects with either treatment were: injection site pain, injection site erythema, hypoglycaemia, vomiting, and headache. One clinical pharmacology study was conducted in 20 subjects with T1DM, each of whom received single doses of LY2963016 and LANTUS; a total of 9 TEAEs were reported by 5 subjects, none of which were considered to be related to study drug.

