10.1. Pharmacokinetic and Pharmacodynamic Evaluations

10.1.1. Samples for Pharmacokinetic and Pharmacodynamic Measurements

During each clamp, venous blood collection (approximately 4 mL) for the determination of the serum concentrations of insulin glargine will begin prior to and continue for up to 24 hours after administration of LY2963016 or LANTUS. Samples (approximately 2.5 mL) will also be taken for the analysis of C-peptide concentrations. Timing of sample collection may be found in [Attachment 1](#); an estimate of total blood volume to be collected during the study may be found in [Attachment 3](#).

The timing of scheduled samples may be adjusted according to clinical needs. The actual collection times will be recorded. Blood samples will be collected via a venous cannula or direct venipuncture. Instructions for the collection and handling of blood samples will be provided by the sponsor. Serum will be obtained by centrifugation and stored at -20°C or below.

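### Does the secondary AUC(0-∞) comparison need a required report of percent extrapolated, given that sampling stops at 24 h?

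*SAP*

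**What the plan says.** - **Sampling.** Protocol 10.1.1 says blood collection for insulin glargine "will begin prior to and continue for up to 24 hours after administration of LY2963016 or LANTUS". In Attachment 1 the samples after 12 h are at 15, 18, 21 and 24 h.
- **Expected profile.** Protocol 5.1 gives a median tmax of 12 h and a half-life of about 10 h from two Phase 1 studies in predominantly Caucasian subjects. It adds: "The serum concentration-time profile was relatively flat and constant over 24 hours". Of the product class it says: "This results in a relatively constant plasma concentration of insulin glargine over 24 hours with no pronounced peak".
- **Analysis.** AUC(0-24) and Cmax are primary. The Protocol synopsis says: "For each PK and PD parameter, the comparison will be evaluated as the ratio of the least-squares geometric means". Protocol 12.1.4.2 makes the AUC(0-∞) and AUC(0-tlast) models optional, while SAP 9.3.2 commits to them: "A similar statistical analysis will be performed for the log-transformed secondary PK parameters".
- **Reporting.** SAP 9.1 states: "Summary statistics and statistical analysis will only be presented for data where detailed in this SAP". SAP 9.3.1 gives the parameter list: "Other PK parameters that will be reported include: AUC from time zero to last measured concentration value", followed by AUC(0-∞), tmax, CL/F, half-life and Vz/F. Neither percent extrapolated nor lambda-z is named.
- **Population.** SAP 8 defines the PK population as "all subjects who received at least one dose of study drug and have evaluable PK data". That is a rule per subject, not per parameter.

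**The concern.** Sampling stops 12 h after the median peak, which is 1.2 half-lives at 10 h. The rest of AUC(0-∞) is C(24)/lambda-z, with lambda-z fitted to at most a few late samples on a curve described as nearly flat. A shallow, noisy slope inflates the tail and widens the interval, and some profiles may yield no slope at all.

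The SAP nevertheless gives AUC(0-∞) the same ratio and 90% CI as the measured AUCs. Its text has no slope rule, and percent extrapolated is not a named output. Read strictly, SAP 9.1 seems to keep that figure out of the summaries. A reader of the report who saw a wider or shifted AUC(0-∞) interval might then not know whether the tail or the products were responsible.

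**Working it through.** The documents state no extrapolated share, so there is no figure of theirs to reproduce.

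**1. Size of the extrapolated share.** Inputs from Protocol 5.1 and 10.1.1: tmax 12 h, half-life 10 h, last sample 24 h. Set the peak to 1.

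- lambda-z = ln 2/10 = 0.0693 per h.
- Share = [C(24)/lambda-z] / [AUC(0-24) + C(24)/lambda-z].
- With a decline from 12 h: C(24) = 2^(-1.2) = 0.435. Area from 12 to 24 h = (1 - 0.435)/0.0693 = 8.15. Tail = 0.435/0.0693 = 6.28.
- With concentrations level to 24 h: C(24) = 1. Tail = 1/0.0693 = 14.43.

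| Assumed shape | AUC(0-24) | Tail | Share |
|---|---|---|---|
| Plateau to 12 h, then decline | 12 + 8.15 = 20.15 | 6.28 | 23.8% |
| Linear rise to 12 h, then decline | 6 + 8.15 = 14.15 | 6.28 | 30.7% |
| Level from 0 to 24 h | 24 | 14.43 | 37.5% |
| Linear rise to 12 h, then level | 6 + 12 = 18 | 14.43 | 44.5% |

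Varying the half-life from 8 to 12 h in the two decline shapes gives 17% to 37%.

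A one-compartment first-order curve with tmax 12 h and elimination half-life 10 h gives 35.5% if the 10 h slope is used. If the slope is fitted to 18-24 h or 15-24 h, the share is 52% or 55%. Those fitted slopes (0.0347 and 0.0306 per h) correspond to half-lives of 20.0 and 22.6 h, about twice the observed 10 h.

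**2. Effect on the interval.** This was simulated on the protocol's sampling times with identical products. The within-subject log SD was sqrt(ln(1 + 0.3926²)) = 0.379, from the stated 39.26% CV. A slope needed at least three samples after the observed peak and had to be negative. Sample noise is an assumption, since the documents give none. The table shows the CI width for AUC(0-∞) relative to AUC(0-24).

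| Shape | 5-10% noise | 15-20% noise |
|---|---|---|
| Decline from 12 h | 1.00-1.06 | 1.06-1.48 |
| First-order curve, fitted slope | about 1.2 (5%) to 2.0 (10%) | 2.6-3.3 |

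On the first-order curve at 10% noise, about 29 of 40 completers have a slope in both periods. These ratios count only such subjects. The SAP's mixed model also keeps single-period data, so they somewhat overstate the loss.

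**3. Can the reader recover the missing figure?**

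- Percent extrapolated = 100 × [1 - AUC(0-tlast)/AUC(0-∞)]. SAP 9.3.1 reports both AUCs, and SAP 13.1 provides for individual derived parameters to three significant figures.
- lambda-z = ln 2/half-life. Half-life is reported, and SAP 2 defines it through lambda-z.
- Writing f for the extrapolated share, log AUC(0-∞) = log AUC(0-tlast) - log(1 - f). On the same profiles, the AUC(0-∞) ratio divided by the AUC(0-tlast) ratio is the geometric mean of (1 - f) for LANTUS over that for LY2963016. Both ratios are planned outputs, so their gap isolates what the tail contributes. If f is the same for both products, it cancels.
- A profile with AUC(0-tlast) but no half-life or AUC(0-∞) is one without a usable slope. The listings show it, and N in the summaries shows how many values are missing.

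**4. Does SAP 9.1 exclude the figure?** No. SAP 9.3.2 itself allows descriptive statistics for further PK parameters at the analysts' discretion, and the list in SAP 9.3.1 is not worded as closed. SAP 9.1 also provides listings of everything in the database.

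**The case for a change.** The strongest case for a change is that the AUC(0-∞) inference is mandatory while the diagnostic that qualifies it is left to discretion. Every shape built on tmax 12 h and a 10 h half-life extrapolates roughly a quarter or more. The interval effect runs from nothing to a doubling at 5-10% noise, and percent extrapolated would help to show which case applies. The cost is a few sentences and one table column. CL/F and Vz/F share the tail if they are derived from AUC(0-∞).

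Much of this stands. The share is substantial, and the SAP's own text has neither a slope rule nor a required summary of percent extrapolated. Two parts do not carry through. The doubling needs fitted half-lives of 20-23 h, against about 10 h in the earlier studies, together with a noise level the documents do not give. The diagnostic, moreover, is simple arithmetic on values already planned for reporting, so discretion does not put it out of reach. Whether a slope rule or a table column is missing at all cannot be established: SAP 9.3.1 places the analysis under the sponsor's divisional PK standards, SAP 3 places output detail in the TFL shells, and neither is among these documents.

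**Conclusion.** No change to the plan is needed. This is a gap that PK analysts fill as a matter of course, and closing it in the SAP would add information the outputs already contain.

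The AUC(0-∞) ratio will probably rest on about 24-31% extrapolated exposure, or about 38-45% if the profile really stays level to 24 h. Both ranges assume that a 12 h tmax and a 10 h half-life carry over to Chinese subjects. The consequence is some loss of precision in a comparison the SAP already ranks as secondary. The loss is negligible with a visible decline and modest noise, and larger only under assumptions that depart from the reported half-life. No bias between the products has been shown, and AUC(0-24) and Cmax do not use the tail. Requiring percent extrapolated, restating the slope rule or relabelling the ratio would alter no estimate, interval or conclusion.

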9.4 Pharmacodynamic Analyses

PD analyses will be conducted on Pharmacodynamic population.

9.4.1 Pharmacodynamic Parameter Estimation

The GIRs and blood glucose values will be recorded on Day 1. A locally weighted scatterplot smoothing (LOESS) function will be applied to all individual GIR versus time profiles in each treatment group and/or period using S-PLUS® software (v8.2). Glucose infusion rates will be used to calculate several PD parameters, including maximum glucose infusion rate (R_{max}), time of R_{max} (tR_{max}), and total amount of glucose infused (G_{tot}). Other parameters namely, the time of first change of GIR postdose ($tRonset$), the time of last measurable GIR ($tRlast$), and the last measurable GIR ($GIRlast$) may be calculated as appropriate.

9.4.2 Pharmacodynamic Statistical Inference

The PD parameters (R_{max} and G_{tot}) will be log-transformed prior to analysis. A linear mixed effects model will be fitted to the data. The model will include subject as a random effect, with period, sequence, and treatment as fixed effects. From the models, the difference in least-squares mean estimates between the 2 treatments and the corresponding 90% CIs for the difference will be estimated and back-transformed from the log scale to provide estimates of the ratios of geometric means and 90% CI for the ratio of these means. The SAS code will be similar to the SAS code used in the PK analysis. Within subject CV for each insulin may be reported if estimable.

Exploratory analyses of other PD parameters may be performed as deemed appropriate, for example, time to R_{max} (tR_{max}), time to first change of GIR postdose ($tRonset$), the time of last measurable GIR ($tRlast$), and the last measurable GIR ($GIRlast$).

